As no animal or cell models exist, our understanding of iMCD is based on analysis of patient samples. These data demonstrate a key role for the PI3K/Akt/mTOR pathway in iMCD pathogenesis: upregulation of serum vascular endothelial growth factor (VEGF) (16/20 patients), ¹¹ activated T cells (n = 6 patients)¹² and elevated serum soluble IL-2 receptor (sIL2R) levels (20/21 patients), and elevated PI3K/Akt/mTOR signaling in lymph node tissue (n = 10 patients)¹ from iMCD patients during disease flare. Additionally, gene-set and pathway analyses of plasma proteomic data identified PI3K signaling as the most significantly enriched canonical pathway during flare compared to remission in six patients, and six of the top 20 most significant

compounds predicted to decrease expression of plasma proteins elevated in flare by enrichment analysis using the Library of Integrative Network-based Cellular Signatures 1000 database target PI3K/Akt/mTOR signaling. ¹³ Most notably, off-label administration of the MTI, sirolimus, to anti-IL6 blockade refractory patients resulted in CBR in two patients experiencing active disease and a prolonged and ongoing remission in one patient² with a history of five disease flares. Based on these experiences, we plan to evaluate the efficacy of sirolimus as a second line therapy to IL-6 blockade therapy in iMCD, and to conduct research studies aimed at better understanding the pathogenesis of iMCD and how blockade of PI3K/Akt/mTOR signaling abrogates the disease. We anticipate the results of this work will establish safety and efficacy profiles of sirolimus as a second line therapy for iMCD.

The primary endpoint of this study is efficacy, as evaluated by CBR criteria. This evaluation criteria was employed as the main efficacy end-point in the open-label Phase I clinical trial of siltuximab,³ and is a composite of clinical (fatigue, anorexia, fever, night sweats and weight gain), radiologic (≥25% bi-dimensional decrease in size of largest lymph node, as measured using Cheson criteria^{14,15} (**Appendix 15.2**), and laboratory (hemoglobin) measures relevant to the clinical management of iMCD. CBR is a well-suited and established criterion for determining efficacy in iMCD.

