4.1 Inclusion Criteria

To be eligible, subjects must meet all of the below inclusion criteria:

- 1. Male or female, age 2-80
- Documented disease history consistent with the diagnostic criteria for iMCD (Appendix 15.1)
 - Confirmation of clinico-histopathological features by licensed pathologist, or a CAS grade of at least 3 in the companion registry study (ACCELERATE)
- 3. Failed/refractory (patient did not achieve sufficient disease control with anti-IL-6 therapy, as determined by the site investigator), relapsed (return of symptoms while on therapy), or inability to tolerate anti-IL-6 or anti-IL-6 receptor therapy
- 4. Evidence of active disease, defined as at least two abnormalities in the criteria comprising the CBR criteria and as defined as abnormal by CTCAE v4.0, including at least one objective measurement (hemoglobin, weight loss, or lymph node size)
 - Hemoglobin < lower limit of normal
 - Fatigue, including fatigue relieved by rest
 - Anorexia, including loss of appetite without alteration in eating habits
 - Fever or night sweats
 - Weight loss ≥ 5% from baseline
 - At least one lymph node meeting modified Cheson criteria (**Appendix 15.2**)
- 5. Ability to consume oral medication in the form of a tablet
- 6. Ability to provide, or for a LAR to provide on their behalf, informed consent prior to any study-specific activities

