7.6 Efficacy Evaluations

The below measures will be used to assess the efficacy of the study intervention and determine if the subject meets criteria for a CBR. All comparisons are against those obtained during the Baseline Visit:

Positive response: Relative to baseline, improvement in at least one of the below criterion without worsening of any single criterion other than hemoglobin on two consecutive study visits.

Negative response: Relative to baseline, worsening of any single criterion other than hemoglobin on two consecutive site visits or failure to achieve improvement for any criterion.

	Hemoglobin	Fatigue	Anorexia	Fever and night sweats	Weight	Lymph node size
Improvement	≥2 g/dL increase without transfusions	≥1 grade decrease by NCI CTCAE version 4.0, May, 2009	≥1 grade decrease by NCI CTCAE version 4.0, May, 2009	≥2°C decrease in fever or return to normal body temperature (37°C) or improvement in night sweats, as assessed by licensed site investigator	≥5% increase not due to increase in new or existing edema	≥25% decrease bi-dimensionally in size of largest lymph node, as measured using Cheson criteria (Appendix 15.2)
Worsening		≥2 grade increase by NCI CTCAE version 4.0, May, 2009	≥2 grade increase by NCI CTCAE version 4.0, May, 2009	≥2°C increase in fever or worsening in night sweats, as assessed by licensed site investigator	≥5% decrease (weight loss not due to decreased edema)	≥25% increase bidimensionally in size of largest lymph node, as measured using Cheson criteria (Appendix 15.2)

The below table provides the CHAP score, which will be used to assess the efficacy of the study intervention. All comparisons are against those obtained during the Baseline Visit:

Score:	0	1	2	3	4
CRP (mg/dL)	<1	≥1, <5	≥5, <10	≥10, <20	≥20
Hemoglobin (g/dL)	≥12	<12, ≥10	<10,≥8	<8	Transfusion dependent
Albumin (g/dL)	≥3	<3,≥2.5	<2.5, ≥2	<2, ≥1.5	<1.5
Performance Score (ECOG)	0	1	2	3	4

The below table provides the modified Cheson response criteria, which will be used to assess the efficacy of the study intervention. Unless otherwise specified, all comparisons are against those obtained during the Baseline Visit:

Complete Response (CR)	All index lesion(s) must have regressed to normal size (≤1.0 cm in		
	their greatest transverse diameter. No new sites of		
	lymphadenopathy >1.5 cm in longest dimension.		
Partial Response (PR)	≥50% decrease in sum of the products of the greatest diameters		

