12.1 Risks

The risk to patients of exposure to the treatment intervention, sirolimus, as related to AEs is relatively low. Sirolimus is an FDA-approved therapy with an established safety profile. Although uncommon, AEs are possible and will be monitored by study staff and licensed site investigators. The most common (≥20%) adverse reactions reported for sirolimus 2 mg/day at a higher incidence than reported for placebo include:

- peripheral edema
- hyperlipidemia, hypercholesterolemia, hypertriglyceridemia
- increased creatinine
- constipation
- hypertension
- abdominal pain / diarrhea
- headache
- arthralgia

Other less common serious complications include:

- angioedema
- leucopenia
- thrombocytosis / thrombocytopenia
- fluid accumulation

- impaired wound healing
- proteinuria
- interstitial lung disease/non-infectious pneumonitis
- calcineurin inhibitor-induced hemolytic uremic syndrome/thrombotic thrombocytopenic purpura/thrombotic microangiopathy

The below table summarizes the known adverse events (AEs) categorized based on timing and frequency:

Known Adverse Events (AEs)									
	Common	Occasional	Rare						
	21-100 out of every 100	5-20 out of every 100	<5 out of every 100						
Immediate: 1-2 days of receiving drug	Nausea, vomiting, oral ulcers	Rash	Allergic reaction (may be life threatening)						
Prompt: 2-3 weeks on drug	Increased cholesterol, increased blood pressure, decreased kidney function, diarrhea	Infections, swelling, weight gain, muscle/joint pain, tremor, acne, rash, abdominal pain, mucositis, headache	Decreased red and white blood cells generated in bone marrow, decreased liver function						
Delayed: Any time later during therapy, excluding the above conditions	Acne		Malignancy resulting from this treatment, destruction of red blood cells and decreased kidney function, interstitial lung disease, hemolytic uremic syndrome/thrombotic thrombocytopenic purpura*						
Late: Any time after completion of treatment			Interstitial lung disease						
Sirolimus was embryo/feto toxic in rats at dosages of 0.1 mg/kg and above (approximately 0.2 to 0.5 is the clinical doses adjusted for body surface area). Embryo/feto toxicity was manifested as mortality and reduced fetal weights (with associated delays in skeletal ossification). Sirolimus is excreted in trace amounts in milk of lactating rats. It is not known whether sirolimus is excreted in human milk.									

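### Drug-related weight gain without edema can be scored as clinical benefit in subjects who had lost no weight, and the plan has no analysis that would show it

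*Combined protocol and SAP*

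**What the plan says.** **The endpoint.** Section 7.6 defines a positive CBR as "improvement in at least one of the below criterion without worsening of any single criterion other than hemoglobin on two consecutive study visits". The negative-response definition ties the two-visit condition to worsening, and I read it that way here. Of the six criteria, weight improves on a "≥5% increase not due to increase in new or existing edema" and worsens on a "≥5% decrease (weight loss not due to decreased edema". The table sets no baseline condition and no age limit for weight. Section 1.1 also describes the component as a gain: "clinical (fatigue, anorexia, fever, night sweats and weight gain".

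**Entry.** Section 4.1 requires two abnormalities among the CBR criteria, "including at least one objective measurement (hemoglobin, weight loss, or lymph node size". The weight item is "Weight loss ≥ 5% from baseline" and is one option among six. A subject can enter on low hemoglobin plus fatigue with no weight loss. Ages run from 2 to 80.

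**Known drug effects.** In the Section 12.1 table, the row for 2 to 3 weeks on drug has a column headed "5-20 out of every 100" that contains "Infections, swelling, weight gain, muscle/joint pain, tremor, acne, rash, abdominal pain, mucositis, headache".

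**Decision rules.** Sections 8 and 8.4 set a null of 0%, a minimum activity of interest of 20%, and a look after 14 subjects reach Visit 9. No response among them means the trial should end. One or more means that enrollment may go on, to 24 evaluable subjects. Section 8.5.1 tests the final CBR rate against historical placebo data.

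**The concern.** The disease abnormality named at entry is weight loss, but the response criterion credits any sufficient gain without edema, whether or not weight had been lost.

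Weight is the only one of the six criteria with both features that make this a problem. Fatigue and anorexia need a fall in grade, so they need a baseline grade to fall from. Fever and night sweats need to be present before they can improve, and the node criterion needs a measured baseline node. Hemoglobin can rise from any level, but Section 12.1 lists reduced red-cell production, so toxicity there works against response. For weight, a listed drug effect moves in the direction of response and no baseline abnormality is needed.

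The comparator cannot correct for this, because historical placebo subjects did not take sirolimus. With a 0% null and a rule satisfied by one response in 14, even a small rate of misclassified gain bears on the interim decision and on the claim of activity.

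**Working it through.** **Inputs.** Interim n = 14, maximum n = 24, null 0%, minimum activity 20%, and continuation possible at one or more responses (Sections 8, 8.4, 8.5.2). Listed frequency of weight gain: 5% to 20% (Section 12.1).

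**The plan's own figure.** If the true rate is 20%, the chance of no response in n subjects is 0.8^n. 0.8^13 = 0.055 and 0.8^14 = 0.044, so 14 is the smallest n that gives less than 0.05. The stated interim size reproduces as a zero-response rule. Under the 0% null the chance of at least one response is zero by construction, so the plan makes no allowance for misclassified responses.

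**What is not known.** Let f be the share of subjects on an otherwise inactive drug who become responders through drug-related weight gain. The gain must reach 5%, not be due to edema, be present at the assessment, and occur without a disqualifying worsening of another criterion. The documents give none of these shares. As an assumption, I multiply the listed 5% to 20% by a combined qualifying share of 25%, 50% or 100%:

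- 5% × 0.25 = 1.25%
- 5% × 0.50 = 2.5%
- 5% × 1.00 = 5% (also 20% × 0.25)
- 20% × 0.50 = 10%
- 20% × 1.00 = 20%

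**Results.** Chance of at least one false responder in 14 is 1 − (1 − f)^14. Expected false responders in 24 is 24f. The last column is the binomial chance of 5 or more in 24, the smallest count with an observed rate of at least 20% (5/24 = 20.8%). The plan sets no success count at 24, so that column is illustrative.

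| f | ≥1 in 14 | Expected in 24 | ≥5 in 24 |
|---|---|---|---|
| 1.25% | 1 − 0.9875^14 = 0.161 | 0.3 | <0.001 |
| 2.5% | 1 − 0.975^14 = 0.298 | 0.6 | <0.001 |
| 5% | 1 − 0.95^14 = 0.512 | 1.2 | 0.006 |
| 10% | 1 − 0.90^14 = 0.771 | 2.4 | 0.085 |
| 20% | 1 − 0.80^14 = 0.956 | 4.8 | 0.540 |

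The interim rule is sensitive to small f. The final response rate is much less so: weight gain alone would be likely to produce an observed rate near 20% only in the last row, where every listed gain at the top of the range qualifies.

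**The case against.** The strongest reply is that the listed 5 to 20 per 100 is not a false-response rate. It covers weight gain of any size, in a row for 2 to 3 weeks on drug, while CBR is judged at Month 6 for the interim and at 12 ± 1 month for the primary endpoint. Section 12.1 does not name the source population, and Sections 1.2.2.2 and 1.3 say that most sirolimus trials also gave cyclosporine, corticosteroids or both. All of this stands. The documents support no lower limit for f above zero.

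A second reply is that Section 7.6 already excludes gain due to edema, and that Section 12.1 also lists peripheral edema and fluid accumulation. A reader might infer from the separate listing of swelling that the listed gain is not fluid. That does not follow; the share left after the exclusion is unknown. On the other side, the plan gives no method for attributing gain to edema, and at a remote Month 6 or Month 12 visit the physical examination is not done (Sections 6.2.7 and 6.2.11).

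Third, one response permits continuation but does not force it. Section 8.5.2 makes it depend on judgment, and the CHAP, symptom-score and nodal endpoints do not credit weight gain. This softens the consequence. It does not tell those deciding to set a weight-only response aside.

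Fourth, a reader might add continuing corticosteroids as a further source of gain. Section 4.2 requires them to have started more than 28 days before enrollment and bars dose increases on study, so that point adds little.

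Finally, the CBR was taken over from an earlier siltuximab trial (Section 1.1), and redefining it would cost comparability. That is a fair reason to leave the primary definition alone.

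**Conclusion.** The gap is real on the text. A gain of at least 5% without edema can make a responder of someone who had lost no weight, and weight gain is a listed drug effect. The rule covers all ages, so it is not only an adult matter.

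The size cannot be fixed from the documents. With f assumed between 1.25% and 10%, the chance that an otherwise inactive drug shows at least one responder in 14 runs from 16% to 77%, with 0.3 to 2.4 false responders expected in 24. The 20% case (96%, 4.8 expected) is an upper bound only, since it needs every listed gain at the top of the range to qualify and persist.

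A reader might infer that toxicity will produce responders at about the plan's 20% minimum, or that any 5% gain counts. The documents support neither: the first holds only at that bound, and the second ignores the edema exclusion and the no-worsening condition. The supported conclusion is narrower. The interim decision and the activity claim could rest on weight-only responses that the plan has no means of separating. This is worth correcting.

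**What to change.** Keep the CBR as adopted for the primary endpoint. In Sections 7.6 and 8.5.1, with a reference from 8.5.2, prespecify that:

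1. subjects whose only improved criterion is weight are counted and reported separately, split by whether they met the weight-loss entry item;
2. CBR is also computed, at the Visit 9 interim and at 12 months, with weight improvement credited only in subjects who met that item, leaving the worsening rule unchanged;
3. the interim decision and the conclusion on activity do not rest on weight-only responders without baseline loss.

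The second rate can only equal or fall below the first, and the difference is exactly the number of weight-only responders without baseline loss. If there is no difference, the concern is closed by the data.

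The eligibility record should show for every subject whether the weight-loss item was met, and against which reference weight, since Section 4.1 does not define it.

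I would not filter on whether the gain is recorded as a drug-related adverse event. Weight regained because the drug works is also drug-related, so an open-label attribution cannot separate benefit from toxicity and could remove true responders.

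The cost is one extra analysis and possibly a slightly lower response rate in it. A limit remains: drug-related gain in subjects who had lost weight would still be credited, and only the separate count in item 1 would show it.

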1.1 Background and Relevant Literature

iMCD is a rare, deadly hematologic illness. Castleman disease describes a group of related diseases defined by characteristic lymph node histopathology - atrophic or hyperplastic germinal centers, prominent follicular dendritic cells, hypervascularization, polyclonal lymphoproliferation, and/or polytypic plasmacytosis. In addition, iMCD patients can experience episodic disease flares characterized by laboratory abnormalities and systemic symptoms, including constitutional symptoms, cytopenias, hepatosplenomegaly, fluid accumulation, and cytokine storm-associated multiple organ system dysfunction.⁴ iMCD's heterogeneous presentation and symptoms, and its overlap with hematologic, oncologic, rheumatologic, and infectious disease makes its diagnosis and treatment difficult. iMCD is diagnosed in approximately 600-1,000 individuals annually in the USA⁵ and 35% of iMCD patients die within five years of diagnosis.⁶ The causes, etiological driver and pathogenic processes that give rise to iMCD are unknown.

Current therapeutic options are limited and provide benefit for only a subset of patients. Blockade of IL-6 signaling with siltuximab, the only FDA-approved iMCD treatment, or tocilizumab, approved for iMCD treatment in Japan, abrogates symptoms and improves lymphadenopathy in a portion of patients. However, 66% of patients in the siltuximab Phase II clinical trial did not meet response criteria, and recent studies found that IL-6 is not significantly elevated in many iMCD patients. Off-label treatment options are empiric, and include corticosteroids, rituximab, and cytotoxic chemotherapy, which have varying efficacies and significant potential toxicities. Identification of molecular and cellular abnormalities for therapeutic targeting is urgently needed for anti-IL-6 blockade refractory patients. Unfortunately, no new drugs are in development.

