5.8 Return or Destruction of Investigational Product

At the completion of the study – following the last enrolled patient's final assessment - there will be a final reconciliation of drug shipped, drug consumed, and drug remaining by IDS and the IP. This reconciliation will be logged on the drug reconciliation form, signed and dated. Any discrepancies noted will be investigated, resolved, and documented prior to return or destruction of unused study drug. Drug destroyed on site will be documented in the study files.

6 Study Procedures

Radiological Imaging

Computed tomography (CT) with contrast or positron emission tomography/CT (PET/CT) scan images conducted as standard of care treatment for iMCD will be centrally reviewed by a radiologist at the University of Pennsylvania. PET/CT will be full body imaging, and CT will include neck, chest, abdomen and pelvis. The site physician should maintain consistency, as is medically appropriate, in imaging modality utilized for each subject to that used at the Baseline Visit.

Blood Draws

No more than 100 mL of blood will be drawn at the Baseline Visit, and no more than 55 mL at each subsequent Visit specifically for research laboratory (i.e. non-clinical health or sirolimus monitoring) purposes. Blood will be drawn into ethylenediaminetetraacetic acid (EDTA) coated tubes (Baseline Visit: 80 mL; subsequent Visits: 40 mL) and serum separator tubes (Baseline Visit: 14 mL; subsequent Visits: 7 mL).

Research samples obtained during on-site visits will be processed at the site or shipped to the University of Pennsylvania for processing. Those obtained during remote visits will be shipped to the University of Pennsylvania for processing. Subjects will be provided with appropriate shipping materials and instructions regarding how to ship research samples to the University of Pennsylvania.

Fecal Sample Collections

Fecal samples will be collected at the Baseline Visit, prior to starting sirolimus, at Week 2, and at Visit 9. Fecal sample collections are optional.

Fluid Sample Collections

Fluid samples, such as those collected during paracentesis, may be collected and stored for research analysis. Samples will be shipped to the University of Pennsylvania or the Children's Hospital of Philadelphia for processing, or may be processed at the site.

Clinical Laboratory Testing

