	(SPD) of index lesion(s), and no new sites of lymphadenopathy >1.5		
	cm in longest dimension.		
Stable Disease (SD)	Failure to achieve a CR or PR (see above) without evidence of		
	progressive disease (see below).		
Progressive Disease (PD)	≥50% increase from nadir in the SPD of any index lesion, or		
	appearance of any new sites of lymphadenopathy that measure >1.5		
	cm in longest dimension during or at the end of therapy.		

MCD-related Overall Symptom Score: In addition to the defined CBR, 34 measures of disease activity will be prospectively evaluated and graded (as per CTCAE version 4.0, May, 2009), which will be used to assess the efficacy of the study intervention. All comparisons are against those obtained during the Baseline Visit:

General MCD-related

- Fatigue
- Malaise
- Hyperhidrosis
- Night sweats
- Fever
- Weight loss
- Anorexia
- Tumor pain
- Dyspnea
- Pruritis

Autoimmune phenomena

- Autoimmune disorder
- Immune system disorder

Fluid retention

- Generalized edema
- Edema face
- Edema limbs
- Edema trunk
- Genital edema
- Localized edema
- Neck edema
- Periorbital edema
- Capillary leak syndrome

- Ascites
- Pleural effusion
- Pericardial effusion

Neuropathy

- Peripheral motor neuropathy
- Peripheral sensory neuropathy
- Nervous system disorder, other

Skin disorders

- Rash acneiform
- Rash maculo-papular
- Papulopustular rash
- Purpura
- Skin hyperpigmentation
- Skin induration
- Skin disorder, other

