15.1 Diagnostic Criteria for iMCD

I. Major Criteria (need both):

Histopathologic lymph node features consistent with the iMCD spectrum (Figure 5). Features along the iMCD spectrum include (need grade 2-3 for either regressive GCs or plasmacytosis at minimum):

Regressed/atrophic/atretic germinal centers, often with expanded mantle zones composed of concentric rings of lymphocytes in an "onion skinning" appearance

Vascularity, often with prominent endothelium in the interfolliduar space and vessels penetrating into the GCs with a "lollipop" appearance

Sheetlike, polytypic plasmacytosis in the interfollicular space

Hyperplastic GCs

2. Enlarged lymph nodes (≥1 cm in short-axis diameter) in ≥2 lymph node stations

II. Minor Criteria (need at least 2 of 11 criteria with at least 1 laboratory criterion)

Laboratory*

- 1. Elevated CRP (>10 mg/L) or ESR (>15 mm/h)†
 - 2. Anemia (hemoglobin <12.5 g/dL for males, hemoglobin <11.5 g/dL for females)
- Thrombocytopenia (platelet count <150 k/μL) or thrombocytosis (platelet count >400 k/μL)
 - 4. Hypoalbuminemia (albumin <3.5 g/dL)
- Renal dysfunction (eGFR <60 mL/min/1.73m²) or proteinuria (total protein 150 mg/24 h or 10 mg/100 ml)
 - Polyclonal hypergammaglobulinemia (total γ globulin or immunoglobulin G > 1700 mg/dL)

Clinical

- 1. Constitutional symptoms: night sweats, fever (>38°C), weight loss, or fatigue (≥2 CTCAE lymphoma score for B-symptoms)
- 2. Large spleen and/or liver
 - 3. Fluid accumulation: edema, anasarca, ascites, or pleural effusion
- 4. Eruptive cherry hemangiomatosis or violaceous papules
 - 5. Lymphocytic interstitial pneumonitis

III. Exclusion Criteria (must rule out each of these diseases that can mimic iMCD)

Infection-related disorders

- 1. HHV-8 (infection can be documented by blood PCR, diagnosis of HHV-8-associated MCD requires positive LANA-1 staining by IHC, which excludes iMCD)
 - 2. Clinical EBV-lymphoproliferative disorders such as infectious mononucleosis or chronic active EBV (detectable EBV viral load not necessarily exclusionary)
- 3. Inflammation and adenopathy caused by other uncontrolled infections (eg, acute or uncontrolled CMV, toxoplasmosis, HIV, active tuberculosis)

Autoimmune/autoinflammatory diseases (requires full clinical criteria, detection of autoimmune antibodies alone is not exclusionary)

- 1. Systemic lupus erythematosus
- 2. Rheumatoid arthritis
- 3. Adult-onset Still disease
 - 4. Juvenile idiopathic arthritis

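### The CBR weight criterion discounts edema only, so, read literally, weight change from ascites (less often effusion) can count as improvement or worsening in the primary endpoint

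*Combined protocol and SAP*

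**What the plan says.** The CBR table in Section 7.6 scores weight as improved on a "≥5% increase not due to increase in new or existing edema". It scores weight as worsened on a "≥5% decrease (weight loss not due to decreased edema". In both directions edema is the only form of fluid that is discounted.

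One criterion can settle the overall result. A positive response is "improvement in at least one of the below criterion without worsening of any single criterion other than hemoglobin on two consecutive study visits". A negative response is "worsening of any single criterion other than hemoglobin on two consecutive site visits or failure to achieve improvement for any criterion". The proportion with a positive CBR at 12 ± 1 month is the primary endpoint (3.2.1, 8.1), and CBR at Visit 9 drives the interim analysis (Section 8, 8.5.2).

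Elsewhere the protocol names other forms of fluid. Appendix 15.1 has the minor criterion "Fluid accumulation: edema, anasarca, ascites, or pleural effusion". The 34-measure symptom score in 7.6 lists ascites, pleural effusion and "Pericardial effusion" as items of their own. Section 1.1 counts "hepatosplenomegaly, fluid accumulation, and cytokine storm-associated multiple organ system dysfunction" among the features of a flare. Section 6 adds: "Fluid samples, such as those collected during paracentesis, may be collected and stored for research analysis".

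**The concern.** Fluid accumulation is part of this disease, and ascites is not an exclusion under 4.2. A weight rule that removes one form of fluid but not the others can therefore move in the wrong direction. Accumulating ascites adds weight, and the improvement cell does not discount it. Resolving ascites removes weight, and the worsening cell does not discount that either. None of the six CBR criteria is a fluid item, so growing ascites is not scored as worsening anywhere else in the CBR. Section 12.1 also lists fluid accumulation among the less common serious complications of sirolimus, apart from peripheral edema. Read literally, an adverse drug effect could be credited as efficacy.

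At stake is the classification of individual subjects in the primary endpoint, in a trial of at most 24 evaluable subjects whose null response rate is 0%.

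**Working it through.** **1. How the protocol uses the terms**

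| Place | Edema | Ascites and effusions |
|---|---|---|
| 7.6, CBR weight, improvement | discounted | not mentioned |
| 7.6, CBR weight, worsening | discounted | not mentioned |
| 7.6, 34-measure score, fluid-retention group | eight items | ascites, pleural effusion and pericardial effusion, one item each |
| 15.1, clinical minor criteria | named | ascites and pleural effusion named separately; pericardial effusion not named |
| 12.1, risks | peripheral edema | fluid accumulation, in a different list |

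No section defines edema to cover ascites or effusion. No section gives a dry-weight or drained-volume rule.

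**2. The rule applied literally**

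- *Gain of at least 5% from ascites, no edema:* the weight cell reads improved. If no criterion other than hemoglobin worsens on two consecutive visits, the CBR is positive. The result is wrong only if no other criterion has improved; otherwise the CBR is positive anyway.
- *Loss of at least 5% from clearance of ascites:* the weight cell reads worsened. If the loss is present on two consecutive visits, the CBR is negative even when other criteria have improved. A single drainage that refills before the next visit does not meet this condition; lasting clearance does.

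**3. How much fluid this takes** (body weights are assumed; 1 L taken as about 1 kg)

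Threshold = 0.05 × body weight.

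- 50 kg: 0.05 × 50 = 2.5 kg
- 60 kg: 3.0 kg
- 70 kg: 3.5 kg
- 80 kg: 4.0 kg
- Children, eligible from age 2, at an assumed 15 to 30 kg: 0.75 to 1.5 kg

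In adults this points to large ascites. A pleural or pericardial effusion alone would less often reach it.

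**4. Effect on the counts**

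- *Final analysis:* one misclassified subject moves the rate by 1/24 = 4.2 percentage points. That is true of any single misclassification, whatever its cause.
- *Interim, the plan's own figure:* with a true rate of 20%, P(0 of 14) = 0.8^14 = 0.044, which agrees with the stated value below 0.05.
- *Interim, with false responders:* suppose the drug is inactive and each subject has probability q of a false positive CBR through weight. Then P(at least 1 of 14) = 1 − (1 − q)^14. The values of q are assumptions; the documents give none.

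| q | P(at least 1 of 14) |
|---|---|
| 1% | 13% |
| 2% | 25% |
| 5% | 51% |
| 10% | 77% |

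The table shows how sensitive a one-responder rule is. It does not estimate what will happen in this trial.

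**The case against.** The strongest reply is that edema can be read loosely. Appendix 15.1 lists anasarca beside edema although anasarca is generalized edema, so a side-by-side list does not prove that the terms exclude one another. The symptom score puts all these items under one heading. An investigator judging what a weight change is due to could sensibly discount obvious ascites. This stands in part: some sites may apply the rule that way. But the protocol has an umbrella term for fluid and does not use it in the weight cells, so the point is left to each site.

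The scenario is also narrow, and that stands. The false-positive route needs litres of non-edema fluid, no other improved criterion, no sustained worsening, and a subject still in the trial rather than withdrawn for progression (6.4, 6.6). The false-negative route needs two consecutive visits. Section 4.2 excludes pulmonary involvement with dyspnea, which makes large pleural effusions less likely.

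Two safeguards could be cited. Section 9.7.2 lets the DSMB adjudicate final outcomes, but this is optional, comes at the end of the study and carries no weight rule, so it does not reach the Visit 9 interim. Section 8.5.2 makes continuation a judgment on safety and appropriateness, so one responder permits further enrollment without compelling it.

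Finally, Section 1.1 presents CBR as an established criterion from the siltuximab Phase I trial, and rewording a component departs from it. That cost is real but small.

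**Conclusion.** The gap is real. Followed literally, the weight criterion can count ascitic weight gain as improvement and lasting clearance of ascites as worsening. Either can decide a subject's primary endpoint under the conditions above. Large ascites is the realistic route in adults.

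A reader might go further and infer that the endpoint systematically scores progression as response, or that the primary result is unusable as it stands. The documents do not support that. They give no frequency of ascites or effusion, and the two errors run in opposite directions, so neither the size nor the sign of the net bias can be computed. Nor does Section 6 show that paracentesis is expected; it only permits storing such fluid.

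What remains is a correctable ambiguity in a primary endpoint. Its practical weight comes from the 0% null and the 0-of-14 rule, under which a single false responder can change the interim reading. The litre figures rest on assumed body weights and 1 L ≈ 1 kg, and the interim probabilities on assumed q.

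**What to change.** In both weight cells of 7.6, replace *edema* with *fluid retention (edema, ascites, pleural or pericardial effusion), including its drainage*. Leave the attribution with the site investigator, as the edema attribution already is. Support it with the fluid-retention grades and the imaging already planned at months 3, 6, 9 and 12. Report CBR under the current edema-only wording as a sensitivity analysis, which keeps the link to the earlier trial.

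The sample size does not change and no new procedure is needed. It would be wrong, however, to assume that the data already planned settle every case. A CTCAE grade does not say how many kilograms are fluid, no section requires the date or volume of a drainage to be recorded, and at remote visits the physical examination and vital signs are not done. One eCRF field for drainage may be needed, and the attribution remains a judgment. The other cost is a minor departure from the earlier trial's CBR wording.
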